3.8 Justification for interventions

The initial starting dose of ferrous sulfate (325 mg po tid) was chosen because this is currently the standard of care as outlined in the KDIGO guidelines for iron deficient individuals with CKD.

The starting dose of ferric citrate needed to balance the requirement to provide sufficient lowering of dietary phosphorus absorption to effect a decrease in FGF23 concentrations (and

thereby help attenuate the rise in hepcidin) while at the same time providing sufficient iron supplementation to treat iron deficiency anemia. While a starting dose of 1 gram of ferric citrate three times a day was considered, in the seminal study comparing the efficacy of ferric citrate vs. placebo in pre-dialysis CKD patients,²⁰ the average final dose of ferric citrate needed to achieve adequate phosphorus reduction was 5.1 grams per day. Therefore, we chose 2 grams three times per day with meals to provide sufficient phosphorus binding effect to lower FGF23 while at the same time providing adequate iron supplementation to compare against ferrous sulfate.

3.9 Procedures and Evaluations

3.9.1 Assessment of Safety

3.9.1.1 Risks and Discomforts

Phlebotomy

Subjects will experience the usual discomfort caused by phlebotomy. The total amount of blood to be collected for the entire study period will be ~150 ml, or ~ ½ cup, less than the volume of blood collected during a single blood donation (500 ml or 2 cups). We will exclude subjects with hemoglobin levels < 7 g/dl for women and < 8 g/dl for men during their screening visit.

Severe hypophosphatemia

Ferrous citrate is an oral phosphorus binder. It is possible that participants taking the prescribed ferrous citrate dose (2 grams three times a day with meals) may develop low serum phosphorus concentrations. In a prior study of 72 individuals with moderate CKD not requiring dialysis being treated with a higher cumulative dose of ferric citrate (5.1 grams/day) than proposed in the current study, there were no events of symptomatic hypophosphatemia, and only two instances of serum phosphorus concentrations falling below 2.5 mg/dL (which resolved on their own). Therefore, the likelihood of severe hypophosphatemia occurring is low, particularly since we will exclude individuals with serum phosphorus concentrations less than 3.0 mg/dL on screening labs. Nonetheless, serum phosphorus concentrations will be monitored through the study. Study drug titration will occur as follows:

- If serum phosphorus concentrations fall to between 2.5 and 3.0 mg/dL, participants will be asked to reduce the dose of ferric citrate to 1 tablet three times a day with meals.
- If serum phosphorus concentrations fall below 2.5 mg/dL, participants will be asked to hold the study drug until serum phosphorus concentrations are above 3.0 mg/dL, and then re-start the study medication at 1 tablet three times a day with meals.
- If serum phosphorus concentrations remain below 3.0 mg/dL despite reduction in study drug dose, the participant will be asked to stop ferric citrate and follow-up blood draws will be obtained two weeks after to ensure that the phosphorus concentration recover to above 3.0 mg/dL.

Elevated iron concentrations: Increases in markers of iron metabolism are anticipated in participants taking either oral ferrous sulfate or ferric citrate. In order to ensure that iron marker concentrations do not increase too high during the course of intervention, both iron saturation (TSAT) and ferritin will be monitored throughout the intervention period. If TSAT rises above 65% or ferritin rises above 1000 ng/ml at any time point the lab results will be repeated within 48 hours. If the results remain elevated, the participant will be asked to stop the study medication but will continue to be followed for the duration of the study visits.

Gastrointestinal upset: It is possible that study participants can develop gastrointestinal upset (dyspepsia, constipation, diarrhea) during the study duration. If this occurs, the following will happen:

- If the participant was randomized to the ferrous sulfate arm, he or she will be asked to reduce the dose of ferrous sulfate to twice a day. If one week after this reduction he or she continues to experience gastrointestinal upset, he or she will be asked to reduce the dose of ferrous sulfate to once a day. If one week after this reduction he or she continues to experience gastrointestinal upset, he or she will be withdrawn from the study.
- If the participant was randomized to the ferric citrate arm, they will be asked to reduce the dose of ferric citrate to 1 gram by mouth three times a day with meals. If he or she continues to experience gastrointestinal upset one week after they make this change, he or she will be withdrawn from the study.

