3.7 Protocol for Handling of Withdrawals

3.7.1 Discontinuation of the study drug

Participants who discontinue the study drug will be expected to continue in the follow-up period and complete all study-specific visits. If a participant is unable to attend a follow-up study visit, contact by telephone is permitted to determine the reason why they are not able to attend a follow-up study visit and determine whether these assessments can be rescheduled.

The study drug can be discontinued if:

- The participant becomes pregnant
- Any investigational drug other than the study drug is used
- Any suspected drug-related adverse events or serious adverse events occur
- If any of the exclusion criteria apply during treatment (e.g., receipt of kidney transplant)
- A significant violation of the study protocol occurs.

Importantly, study drugs can be temporarily discontinued for reasons as outlined in section 3.9.1.1 below.

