3.7.2 Discontinuation from the study

Participants can be withdrawn from the study at any time if they specifically ask to withdraw or if, in the opinion of the study PI, continuation of the study would be harmful to the participant. In addition, a participant can be withdrawn at any time by the PI if he or she repeatedly violates study protocol.

Participants withdrawn prior to the final scheduled visit will be asked to attend a close-out visit in which they provide blood and urine samples (for final analyses), and complete documentation related to the development of any adverse events.

If the withdrawal is due to an adverse event, participants will be followed until the event resolves or it is shown that the adverse event was not due to the study medication.

Randomized participants who withdraw prematurely will not be replaced. A participant who withdraws after signing informed consent but before randomization can be replaced.

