4.3 Statistical Plan

To compare the baseline characteristics between the two groups, student's t-test or chi square test will be used for parametric and non-parametric variables respectively. Subjects' baseline values will serve as the reference for comparison with changes post-intervention. Longitudinal changes in the primary outcome variables will be examined using repeated measures linear mixed models. In these models, time and treatment group will be the fixed variables and participants will be modeled as random terms. We will first test for a time by treatment group interaction to determine whether the change in the outcome variables over time differs by treatment group assignment. If we detect a statistically significant interaction, we will stratify the analysis by treatment group and test the main effect of time in stratified models. If we do not detect a significant interaction, we will remove the interaction term from the model and will test for the main effects of time and treatment group. If we find any differences in baseline characteristics despite randomization, we will adjust for these covariates in secondary models. We will analyze data using an intention-to-treat principle such that all randomized participants who received at least one dose of study medication and had at least one post-baseline assessment will be included to assess efficacy.

4.4 Sample Size Calculation:

The sample size estimation is powered to detect a significant difference in the change in ferritin in response to oral ferric citrate vs ferrous sulfate challenge. In a prior study, treatment with ferric citrate for 12 weeks raised serum ferritin by 77.5 [95%CI 56.2-98.7] as compared to placebo. To detect as small as a 20% lower rise in ferritin in individuals taking ferrous sulfate vs. ferric citrate over a similar period of intervention, we would need recruit 60 individuals overall (30 per arm) assuming a type I error of 0.05 and a power of 80%. This will also provide ample power to detect at least a 20% difference in the change in TSAT as well. While we also plan on examining changes in hepcidin in this protocol, we did not specifically power the analysis for this outcome variable as it is a secondary outcome.

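### Persistent GI upset leads to withdrawal from the study rather than from study drug, contrary to section 3.7.1, so scheduled week-6 or week-12 TSAT and ferritin values go uncollected

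*Combined protocol and SAP*

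**What the plan says.** The GI rule in section 3.9.1.1 has one bullet per arm. On ferric citrate there is a single dose reduction, and a participant who "continues to experience gastrointestinal upset one week after they make this change, he or she will be withdrawn from the study". On ferrous sulfate there are two reductions, first to two daily doses and later to one, before the same outcome: "If one week after this reduction he or she continues to experience gastrointestinal upset, he or she will be withdrawn from the study".

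Other parts of the protocol separate stopping drug from leaving the study:

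- Section 3.7.1: "Participants who discontinue the study drug will be expected to continue in the follow-up period and complete all study-specific visits". Its list of reasons for stopping drug includes suspected drug-related adverse events.
- Section 3.9.1.1, elevated iron: "the participant will be asked to stop the study medication but will continue to be followed for the duration of the study visits".

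For those who do leave, section 3.7.2 says: "Participants withdrawn prior to the final scheduled visit will be asked to attend a close-out visit in which they provide blood and urine samples". It adds that these samples are meant for the final analyses, and that a participant who leaves because of an adverse event is followed until the event resolves or is shown not to be due to the study medication. It also says: "Randomized participants who withdraw prematurely will not be replaced".

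Section 4.1 makes TSAT and ferritin the primary outcomes, and section 3.1 schedules samples at baseline and weeks 2, 6 and 12. Section 4.3 plans linear mixed models under an intention-to-treat principle, for randomised participants who took at least one dose and "had at least one post-baseline assessment will be included to assess efficacy".

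**The concern.** A participant whose persistent GI upset is thought to come from the study iron falls under two instructions. Section 3.7.1 stops the drug and keeps the visits; section 3.9.1.1 ends participation. If site staff follow the GI rule as written, sampling of the primary outcomes ends for a reason connected with treatment, in a plan that invokes intention-to-treat.

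The mixed model then has to treat the uncollected values as missing at random. In effect, it assumes that leavers would have continued like similar participants who stayed on drug. They will have stopped the iron, or switched to another product, so that assumption is open to doubt. The data that could check it would not have been collected.

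**Working it through.** **1. The rules side by side**

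| Trigger | Drug | Scheduled outcome visits afterwards |
|---|---|---|
| Suspected drug-related adverse event (3.7.1) | Can be stopped | Continue |
| High TSAT or ferritin, confirmed (3.9.1.1) | Stopped | Continue |
| Persistent GI upset (3.9.1.1) | Ends with participation | End; one close-out sample requested (3.7.2) |

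The adverse-event follow-up in 3.7.2 concerns the event and does not provide for iron sampling at weeks 6 and 12.

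**2. Which visits are missed**

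The rule implies exit one week after the first dose cut on ferric citrate and two weeks after it on ferrous sulfate. The protocol does not say when that cut is made.

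- *Cut made at a study visit.* At week 2, exit is at week 3 or week 4, and both arms miss weeks 6 and 12. At week 6, exit is at week 7 or week 8, and both arms miss week 12 only.
- *Cut made on the day of onset.* Both later visits are missed for onset before day 42 − 7 = 35 (ferric citrate) or 42 − 14 = 28 (ferrous sulfate). Week 12 is missed for onset before day 84 − 7 = 77 or 84 − 14 = 70. Ferric citrate onset before day 14 − 7 = 7 gives exit before week 2. The arms differ only for onset on days 0–6, 28–34 and 70–76.

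**3. The plan's own figure and the standard error**

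Section 4.4 gives 30 per arm for a difference of 0.20 × 77.5 = 15.5 ng/mL, with no SD. Taking the SD as the half-width of the quoted interval, (98.7 − 56.2)/2 = 21.25, gives 2 × (1.960 + 0.842)² × 21.25² / 15.5² = 29.5, so 30 per arm (two-sided 0.05, 80% power). The figure reproduces. However, a half-width measures the precision of a mean and is doubtful as a between-person SD.

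Read as a 95% interval, it implies a standard error (SE) of 21.25/1.96 = 10.84. Section 3.9.1.1 mentions 72 treated individuals in a prior study. Assume that it is the same study:

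- 72 per arm: SD = 10.84 × √36 = 65.05; SE at 30 per arm = 65.05 × √(2/30) = 16.8.
- 72 in total (36 per arm): SD = 10.84 × √18 = 46.0; SE = 11.9.
- SD 21.25 as above: SE = 5.5.

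**4. Illustrative shift in the week-12 ferritin difference**

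Assumptions: the on-drug rise is R = 77.5 on ferric citrate (a placebo-adjusted figure used as a stand-in) and 0.8R = 62 on ferrous sulfate. Proportions q_FC and q_FS withdraw and would have kept a share k of the rise. No close-out sample is used.

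Shift = (1 − k) × R × (q_FC − 0.8 q_FS)

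| q_FC, q_FS (assumed) | k = 0 | k = 0.5 | k = 1.2 (other iron) |
|---|---|---|---|
| 10%, 5% | +4.65 | +2.33 | −0.93 |
| 10%, 10% | +1.55 | +0.78 | −0.31 |
| 5%, 10% | −2.33 | −1.16 | +0.46 |

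The shift is zero when k = 1 or q_FS = 1.25 q_FC. The +4.65 case is 0.28 SE at SD 65.05, 0.39 SE at SD 46.0 and 0.85 SE at SD 21.25. With R at its upper limit, 98.7 × 0.06 = 5.92, which is 0.35 or 0.50 SE for the first two SDs. For precision, 27 instead of 30 per arm raises the SE by √(30/27) = 1.054, about 5%.

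**5. Does the close-out slot matter?**

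Expected generalised least-squares estimate, assuming a random intercept (between-person SD 80, within-person SD 46), categorical time by arm, a linear rise, 10% and 5% leavers, and close-out at week 3 (ferric citrate) or week 4 (ferrous sulfate):

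- close-out not used: 15.5
- entered as week 6: 15.07
- entered as week 12: 11.75

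The all-randomised value is 15.5 − 4.65 = 10.85 if no gain is kept and 15.5 − 2.33 = 13.17 (13.18 before rounding) if half is kept. Entering the sample as week 12 therefore leaves +0.90 in the first case and −1.42 in the second.

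**The case against.** The strongest reply is that no consequence has been shown. Section 3.2.3 excludes known GI disorders and severe reactions to oral iron, so cases may be few. The close-out sample is intended for analysis, the mixed model uses the earlier visits, and the illustrative shifts are mostly small and of either sign. Section 3.7.2 also contemplates withdrawal for an adverse event, so the GI rule can be read as a specific rule overriding a general one. All of this stands, and it limits the point to a cheap improvement. It does not explain why GI upset should be handled differently from a drug-related event under 3.7.1.

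A second reply is that the harm and the cost of the fix are one quantity. At 10% in both arms with no gain kept, the shift is 1.55, and the dilution after the fix is 15.5 − 13.95 = 1.55. That is correct: it is the gap between an on-drug target and an all-randomised target. Section 4.3 invokes intention-to-treat, which favours the second, but it says nothing explicit about off-drug values.

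Three stronger readings are tempting:

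- *That the loss is unequal between arms because ferric citrate has one reduction step and ferrous sulfate two.* This needs the dose to be cut near the day of onset. Sections 3.4.4 to 3.4.6 and 3.9.2 record events at visits. The one-week rechecks imply some contact between visits, but the protocol does not state when the first cut is made. With cuts made at visits, both arms miss the same visits.
- *That every other stopping rule preserves outcome sampling.* Under the hypophosphatemia rule, "the participant will be asked to stop ferric citrate and follow-up blood draws will be obtained two weeks after", but that is a check that phosphorus has recovered and does not itself promise outcome visits.
- *That the shift is at most about a third of an SE.* That holds only for SD 65.05. The other SDs give larger ratios, so the ratios support no firm ranking.

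**Conclusion.** The inconsistency is real and can be read directly from sections 3.7.1, 3.7.2 and 3.9.1.1. Following the GI rule as written leaves remaining scheduled week-6 and/or week-12 primary-outcome values uncollected, leavers are not replaced, and 4.3 does not say which visit a close-out sample counts as.

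A reader might infer that the treatment comparison will be biased. The documents do not support that: they give no GI withdrawal rate, no information on what leavers' iron indices do next, and no SD. The illustration runs from −2.3 to +4.7 ng/mL at R = 77.5, with withdrawal rates and retained gain all assumed, and it describes a week-12 contrast, whereas 4.3 first tests a time-by-treatment interaction across visits. Frequency, size and direction are undetermined, and the effect may be small.

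The change is worth making because values not drawn cannot be recovered later and drawing them costs little. Label: cheap improvement.

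**What to change.** In both GI bullets of 3.9.1.1, replace the instruction to withdraw with: *stop study drug and continue all scheduled visits to week 12*. Keep the dose-reduction steps. Participants may still leave on request or if continuing would be harmful, as 3.7.2 already allows, so no protection is removed.

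In 4.3, state that values collected after stopping drug are analysed as randomised, and specify how a close-out sample from anyone who still leaves enters the model. Record non-study iron taken after stopping.

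Cost: a wording change and at most two already scheduled visits per affected participant (an assumed 10% would be about 3 of 30 per arm). Downside: off-drug values may slightly dilute the observed arm difference, for example 15.5 × 0.9 = 13.95 ng/mL at an assumed 10% in both arms with no gain kept. Values on other iron may also affect it, and the record of non-study iron would help readers interpret this.

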3.9.2 Adverse events

Any adverse medical event (sign/symptom/laboratory results) occurring in a research participant will be captured in standardized forms at each follow-up study visit. Adverse events will be coded using the Medical Dictionary for Regulatory Activities (MedDRA) and will be grouped by SMQs.

A serious adverse event includes any event that results in a death, is life-threatening, results in an inpatient hospitalization, results in a significant disability, or in any other serious injury or prolongs the hospitalization as judged by the PI.

3.9.2.1 Documentation of adverse events

Each adverse event will be documented according to the following criteria:

- Intensity
 - Mild: transient in nature, minor interference in activities of daily living
 - Moderate: serious impediment to normal daily activities
 - Severe: prevents normal activities
- Relationship with study drug exposure
 - The PI will determine whether the adverse event was likely or unlikely related to study drug exposure. If the latter, the most likely alternative explanation for the adverse event will be documented in case report forms.
- Action taken
 - The study staff will document whether any action was taken to resolve the adverse event.

3.9.3 Adverse event reporting

The principal investigator will report any adverse events to the IRB within the required time frame for reporting as outlined below:

- For serious adverse events, the principal investigator will report the events to the IRB immediately (within 24 hours of event) by telephone, fax or email. The principal investigator will then submit a full written report using the IRB Adverse Event Form within 10 working days or 14 calendar days.
- For mild to moderate adverse events that are unexpected, but are thought to be related to the intervention, the principal investigator will report the events to the IRB in writing using the IRB Adverse Event Form within 20 working days or 30 calendar days.

- For mild to moderate adverse events that are both unexpected and are thought to be unrelated to the intervention, the principal investigator will summarize the events in a progress report for the annual continuing review.
- For mild to moderate and expected adverse events, the principal investigator will summarize the events in a progress report for the annual continuing review.

The principal investigator will also report all serious adverse events that occur 2 weeks after active study participation and are thought to be related to the study intervention.

4 Statistical Analyses

4.1 Primary outcome

The primary outcome variables for this analysis will be transferrin saturation (TSAT) and ferritin concentrations.

4.2 Secondary outcome variables

The secondary outcome variables will include hemoglobin, serum hepcidin, serum erythroferrone, serum phosphorus and plasma FGF23 concentrations. Serum hemoglobin, phosphorus and plasma FGF23 concentrations will be measured in all participants at all visits depending on available samples. Serum hepcidin and erythroferrone will be examined in a subset of participants (n=30) with samples available at the baseline visit, week 2 and week 6 or 12.

4.3 Statistical Plan

To compare the baseline characteristics between the two groups, student's t-test or chi square test will be used for parametric and non-parametric variables respectively. Subjects' baseline values will serve as the reference for comparison with changes post-intervention. Longitudinal changes in the primary outcome variables will be examined using repeated measures linear mixed models. In these models, time and treatment group will be the fixed variables and participants will be modeled as random terms. We will first test for a time by treatment group interaction to determine whether the change in the outcome variables over time differs by treatment group assignment. If we detect a statistically significant interaction, we will stratify the analysis by treatment group and test the main effect of time in stratified models. If we do not detect a significant interaction, we will remove the interaction term from the model and will test for the main effects of time and treatment group. If we find any differences in baseline characteristics despite randomization, we will adjust for these covariates in secondary models. We will analyze data using an intention-to-treat principle such that all randomized participants who received at least one dose of study medication and had at least one post-baseline assessment will be included to assess efficacy.

4.4 Sample Size Calculation:

The sample size estimation is powered to detect a significant difference in the change in ferritin in response to oral ferric citrate vs ferrous sulfate challenge. In a prior study, treatment with ferric citrate for 12 weeks raised serum ferritin by 77.5 [95%CI 56.2-98.7] as compared to placebo. To detect as small as a 20% lower rise in ferritin in individuals taking ferrous sulfate vs. ferric citrate over a similar period of intervention, we would need recruit 60 individuals overall (30 per arm) assuming a type I error of 0.05 and a power of 80%. This will also provide ample power to detect at least a 20% difference in the change in TSAT as well. While we also plan on examining changes in hepcidin in this protocol, we did not specifically power the analysis for this outcome variable as it is a secondary outcome.

A prior randomized, controlled study of patients with stage 3-5 CKD (eGFR 10-59 ml/min/1.73m²) showed that treatment with oral ferrous sulfate (325 mg po bid) resulted in a mean increase in hemoglobin of 0.2 ± 0.9 g/dL (Agarwal R et al, Am J Nephrol 26:445-454, 2006). If we assume that treatment with ferric citrate for 12 weeks will increase hemoglobin by 0.6 ± 0.4 mg/dL (Block et al, Am J Kidney Dis 65(5):728-736), the current sample size of 60 participants overall will provide ~60% power to detect a mean difference in hemoglobin increase of 0.4 ± 0.7 between the two groups.

References

3. Ganz T. Heparin, a key regulator of iron metabolism and mediator of anemia of inflammation. Blood 2003;102:783-8.
10. Nemeth E. Anti-heparin therapy for iron-restricted anemias. Blood 2013;122:2929-31.

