3.1 General overview

- Randomized, open-label study of ferric citrate vs. ferrous sulfate in patients with moderate to severe CKD (eGFR 15 – 45 ml/min/1.73m²).
- Participants will be recruited from the outpatient nephrology clinics at the University of Alabama at Birmingham (UAB).
- Written informed consent will be obtained at the screening visit after the study has been explained in full.
- Participants taking oral iron supplements at the time of the screening visit will undergo a four week wash-out period prior to beginning study medications.
- After eligibility is confirmed following the screening visit (and wash-out period if necessary), participants will be randomly assigned 1:1 to take ferric citrate at a dose of 2 grams three times a day with meals (n=30) or ferrous sulfate at a dose of 325 mg by mouth three times a day between meals (n=30) for a total of twelve weeks.
- Fasting blood and urine samples will be collected at baseline and two, six and 12 weeks after baseline for measurement of study outcome variables. Data for the outcome variables as well as safety will be collected at these time points.
- The study will end at 12 weeks, a final blood and urine sample will be drawn and intervention will be stopped.

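### Section 4.3 leaves the within-participant covariance and the coding of time open; read as a random-intercept model, it can understate the standard error of the week-12 difference in change

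*Combined protocol and SAP*

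**What the plan says.** Section 4.1 sets the endpoints: "The primary outcome variables for this analysis will be transferrin saturation (TSAT) and ferritin concentrations". Section 3.1 sets the visits: "Fasting blood and urine samples will be collected at baseline and two, six and 12 weeks after baseline". Section 4.3 gives the model: "Longitudinal changes in the primary outcome variables will be examined using repeated measures linear mixed models", where "time and treatment group will be the fixed variables and participants will be modeled as random terms". Baseline is the comparator: "baseline values will serve as the reference for comparison with changes post-intervention".

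The tests follow in sequence. "We will first test for a time by treatment group interaction". If it is significant, "we will stratify the analysis by treatment group and test the main effect of time in stratified models". If it is not, the interaction term is dropped and the analysts "will test for the main effects of time and treatment group".

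Section 4.3 does not give a residual covariance structure, a random slope, a robust standard error or a degrees-of-freedom method. It does not say whether time is a factor or a continuous variable, and it names no between-arm contrast at week 12. Section 4.4 nevertheless sizes the trial on the between-arm difference in ferritin change over a 12-week period.

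**The concern.** A model whose only random term is a participant intercept has two covariance parameters. It forces the same variance at every visit and the same correlation between weeks 0 and 2 as between weeks 0 and 12. The variance of a change is then the same over 2 weeks as over 12.

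That is a strong assumption for markers that accumulate under treatment. Sections 3.9.1.1 and 3.7.1 also allow doses to be reduced or stopped while participants who stop study drug keep attending, so exposure can diverge as follow-up lengthens. If the variance of change does grow with the interval, the model averages it over all visit pairs. The week-12 interval comes out too narrow and the week-2 interval too wide.

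The 12-week difference is the quantity the trial was sized on and the one readers will look for. If time is entered as a linear term, the plan's own first test, which decides the branch that follows, is exposed as well.

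**Working it through.** **The plan's own figures.** No stated figure depends on the covariance. The one power statement with complete inputs is for hemoglobin (section 4.4): difference 0.4, SD 0.7, 30 per arm. Then 0.4 / (0.7 × √(2/30)) = 2.213, and Φ(2.213 − 1.96) = 0.60, matching the stated ~60%. It treats the result as a two-sample comparison of change. The ferritin sample size cannot be reproduced because no SD is given.

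**Inputs.** From the documents: 30 per arm, visits at weeks 0, 2, 6 and 12, type I error 0.05. Assumed: two-sided test, complete data, no true effect, and every covariance below.

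**Formula.** With balanced data, the random-intercept model estimates the variance of any change as the mean of Var(Yi − Yj) over the six visit pairs. The true value for week 12 is Var(Y12 − Y0). So

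- SE ratio (model/true) = √[mean over pairs of Var(Yi − Yj) / Var(Y12 − Y0)]
- actual type I error ≈ 2 × [1 − Φ(1.96 × SE ratio)]

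**Example 1: correlation 0.95 per week, constant variance 1.** The lags are 2, 6, 12, 4, 10 and 6 weeks, with correlations 0.9025, 0.7351, 0.5404, 0.8145, 0.5987 and 0.7351 (mean 0.7211). The model variance of change is 2 × (1 − 0.7211) = 0.558. The true week-12 value is 2 × (1 − 0.5404) = 0.919. The SE ratio is √(0.558/0.919) = 0.779, so type I error ≈ 12.7%. At week 2 the true value is 2 × (1 − 0.9025) = 0.195, so that SE is overstated by √(0.558/0.195) = 1.69.

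**Example 2: random slopes, SD 1.0 at week 12 (in baseline SDs), residual variance 0.3.** The mean of (lag/12)² over the six pairs is 336/6/144 = 0.389. The model variance is 0.389 + 0.6 = 0.989 and the true value is 1 + 0.6 = 1.6. The SE ratio is 0.786, so type I error ≈ 12.3%.

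**Simulation.** 20,000 null trials per scenario, random-intercept fit, nominal 5%:

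| Assumed covariance | Week-12 change contrast | Interaction, linear time |
|---|---|---|
| Compound symmetry | 4.9% | 4.9% |
| Correlation 0.90 / 0.95 / 0.98 per week | 11.0 / 12.3 / 14.1% | 14.3 / 16.3 / 18.0% |
| 0.95 per week, 30% measurement noise | 8.0% | 9.4% |
| Random slopes, SD 0.25 at week 12 | 5.7% | 5.9% |
| Random slopes, SD 0.5 / 1.0 / 1.5 at week 12 | 7.9 / 12.0 / 16.0% | 8.3 / 14.1 / 18.9% |

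Further scenarios, also with 20,000 trials each:

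- Equal correlation with SD rising 1.5-fold or 2-fold by week 12: 7% or 10% for the week-12 change contrast.
- Change from baseline as the outcome, correlation 0.95 per week and SD doubling: 17.0% for the week-12 contrast.
- Interaction with categorical time (3 df): about 5-8% across these covariances.
- Group main effect: about 5% throughout.
- An artificial limit with almost no residual noise gives higher figures (22-23% for the week-12 change contrast). It is left out of the ranges quoted.

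**After the fix.** With complete data, the unstructured week-12 contrast equals a two-sample t-test on change (58 df). Its type I error was 4.8-5.3% in every scenario.

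**The case against.** The strongest reply is that the inflated test is not in the plan. Section 4.3 tests the interaction, then within-arm time effects or main effects. With time as a factor, the between-arm tests it names run at about 5-8% and about 5%. A week-12 contrast read only after a significant categorical interaction could not reject jointly more often than that interaction does. This stands. A reader might infer that the trial's planned week-12 comparison runs at 8-17%, but no such comparison is specified. What remains is that the sizing points to a 12-week difference, and that the text also permits linear time, where the interaction itself is affected.

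Second, compound symmetry is an inference. The wording does not exclude random slopes, a structured residual or robust standard errors. This also stands: the documents show an unspecified covariance, not a wrong one deliberately chosen. If something richer was intended, section 4.3 still needs to say so.

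Third, direction and size depend on the true covariance, on which the documents are silent. A reader might infer that the standard error is always understated. It is not: under compound symmetry it is correct, and under mild slopes the error rate is under 6%. The problem also belongs to the change from baseline. A cross-sectional week-12 difference stays near 5% when variance is constant, even with decaying correlation, and drops to 1.6% (standard error overstated) if the SD falls to 0.7 of its baseline value.

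**Conclusion.** The point holds in conditional form, with medium confidence. Read naturally, section 4.3 rests on an equal-variance, equal-correlation assumption for unequally spaced visits and has no stated safeguard. If correlation decays or participants respond at different rates, a between-arm test of week-12 change from that model has a type I error of roughly 6-17%. With linear time, the plan's gatekeeping interaction test has about 6-19%. Both return to about 5% under compound symmetry. These ranges rest on assumed covariances, complete data and 30 per arm; they show what is possible and do not estimate this trial's error rate. The documents do not support a claim that the planned analysis as a whole is inflated to that degree.

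**What to change.** In section 4.3:

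- Enter visit as a categorical fixed effect, with baseline as one of the four repeated measures.
- Use an unstructured within-participant covariance across the four visits, fitted by REML with Kenward-Roger degrees of freedom.
- Pre-specify a fallback if the model does not converge, such as heterogeneous Toeplitz or random intercept plus slope.
- Name the between-arm difference in change from baseline at week 12 as the primary contrast for TSAT and for ferritin.

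This matches the analysis to the quantity in section 4.4. It changes SAP wording and model code only; no visits, data or participants are added. The model has 10 covariance parameters instead of 2. If compound symmetry truly holds, the power loss is about 1 point (79.6% against 80.4% in simulation).
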